CONTROLLED PHONATION AND VOCAL REST PROGRAMS AFTER ACUTE VOCAL EXERTION IN HEALTHY ADULTS

NCT03762993

07/22/2020

APPLICATION NARRATIVE FORM

Purdue University, Institutional Review Board

A. PROPOSED RESEARCH RATIONALE

Roughly 17.9 million adults in the United States are affected by voice disorders annually.¹ These disorders reduce quality of life and social interaction.² Voice disorders represent a significant financial burden, costing hundreds of millions of dollars in medical bills and resulting in an average of what is estimated to be as many as 39.2 work days per year.³ Although the etiologies of voice disorders vary, speakers with voice problems consistently report vocal fatigue and increased effort to speak as the first symptoms. These speakers are often advised to cease voice use partially or completely, however, this may not be realistic given their occupation and the high cost to quality of life by not speaking.⁴ The question then becomes, what should be done to mitigate the negative symptoms of voice problems when they occur, both to ease subsequent vocal function and to avoid eventual voice disorders.

In other anatomical subsystems, the idea of “cool down” following exertion is common. Data from multiple tissue types suggest that cool down following acute trauma may improve recovery. Emerging data suggest that a vocal cool down, may have a beneficial effect on vocal fold wound healing.⁵ This work has primarily been done on animal models, however, preliminary data gathered in human subjects suggests that some individuals benefit from a cool down following vocally tiring events.⁶ However, this question has not been systematically studied investigated in a rigorous manner that also enables us to understand the underlying mechanisms of this beneficial effect.

The proposed study will examine the effects of vocal cool down following exertion on voice measures and respiratory kinematics. Each speaker will also participate in a vocal rest experiment so we can compare cool down with vocal rest. Specifically, we seek to determine if a vocal cool down can mitigate the negative effects of a vocally tiring task as compared to vocal rest. We will assess voice measures and respiratory kinematics repeatedly to identify underlying mechanisms.

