In preparation for each participant, the rigid endoscope will be wet disinfected with Cidex OPA (0.55% ortho-phthalaldehyde) and rinsed in water. A microphone will be placed externally on the participant's neck and secured comfortably with a Velcro strap. The participant's tongue will be draped with sterile gauze and held by the investigator who will be washed and gloved. The endoscope will be inserted through the mouth. The participant will be asked to produce an /ee/ sound with the endoscope in place. Some participants with a hyperactive gag may feel uncomfortable with the endoscope in place. The chance of eliciting a gag reflex will be minimized by changing the position of the endoscope. The endoscope will be placed in the participant's mouth for no more than 3 minutes. The participant will be able to breathe comfortably through their nose during the whole time. The scope may be placed up to four times per session. There are no particular risks associated with having the scope placed orally multiple times in a single day. Some subjects may experience increased gag reflex, but this is temporary and will not last after the scope is removed. Any participant who experiences discomfort or anxiety may withdraw from the study.

Voice measures will be obtained. Participants will wear a headset microphone. Participants will be asked to glide up and down their pitch range, produce different sounds at different loudness and pitch levels and sing some common songs. We will also collect the air pressure used for speaking and singing. The participant will be seated comfortably and a clean face mask with approximately a 2" length of plastic tubing will be placed around participant's mouth and nose. Participant's nostrils may be occluded. The airflow mask is vented with large screen covered holes so that it does not interfere with breathing or speaking. Each participant will receive a new disposable plastic tube. Participants will produce different sounds at different loudness and pitch levels with the mask in place. Finally, participants will use visual analog scales to rate how they feel about their voice.

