Respiratory kinematic data will also be collected. To collect these data, respiratory bands will be placed around the subject's rib cage and abdomen. These bands will be attached with tape over clothing and do not pose any risk to the participant. Participants will be seated and asked to remain relatively still throughout these procedures. Next calibration will be completed. In order to achieve calibration, each participant will be asked to perform the following tasks while the movements of the chest wall and abdomen are recorded; quiet breathing, breathing while thinking a sentence silently, breathing in and out as much as possible, pulling the stomach in and pushing the stomach out as much as possible. The breathing tasks will be performed into a cardboard tube attached to a filter which is placed in the subject's mouth. These tubes are disposed of following each use and the filters disinfected. In addition, nose clips may be used during these tasks and are again disposed of after each use. Following calibration, subjects will be asked to read prepared sentences while wearing the respiratory bands.

In summary, spirometry will be collected one time per day, on both days. Videostroboscopy, voice measures and respiratory measures will be collected at 4 different times on each day. These times are (1) before the vocal exertion (see below; (2) after the vocal exertion (3) before vocal exertion (4) after vocal exertion.

Vocal Exertion Task: For this task, subjects will produce loud sounds for 15 minutes. Subjects will complete a vocal exertion task two times on each day.

Measures: Videostroboscopy, voice measures, and respiratory kinematics will be reobtained after the vocal exertion task.

Cool Down versus Vocal Rest: Participants will be counterbalanced to cool down or vocal rest such that each participant will complete both on different days. Each will take less than 15 minutes. For vocal rest, subjects will not speak. For cool down, subjects will complete voice exercises. These exercises are commonly utilized in clinical settings in order to help patients reduce throat tension and speak more efficiently. The exercises involve speaking and singing long vowels and pitch glides both with and without a straw. In addition, participants will hum and speak sentences with specific consonants (e.g. m and p). Each participant will be provided a new straw.

Measures: Videostroboscopy, voice measures, and respiratory kinematics will be obtained.

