J. STATISTICAL ANALYSIS PLAN

Statistical analysis will be conducted using SAS (Version 9.4, 2013). Power analysis indicates an N of 30 subjects will be sufficient to answer study questions with reasonable statistical power. Dependent measures will be analyzed using linear mixed effect models. Fixed factors included in the statistical model will include time (baseline, post exertion task 1, post restorative strategy, post exertion task 2) and restoration strategy (controlled phonation or vocal rest). A time and restoration strategy interaction will also be included in the model. Participant will be included as a random factor in order to control for individual variation. Alpha level for significance will be set at $p < .05$. Tukey HSD tests will be used on post-hoc comparisons. In addition, Cohen's d for repeated measures will be calculated on significant post-hoc comparisons using the Cohen's d calculator for repeated measure designs developed by Psychometric.de (https://www.psychometrica.de/effect_size.html).

References

1. Bhattacharya, N. The prevalence of voice problems among adults in the United States. *The Laryngoscope* **124**, 2359–2362 (2014).
4. Rousseau, B. *et al.* Compliance and quality of life in patients on prescribed voice rest. *Otolaryngol.-- Head Neck Surg.* **144**, 104–107 (2011).
5. Branski, R. *et al.* Dynamic biomechanical strain inhibits IL-1beta-induced inflammation in vocal fold fibroblasts. *J. Voice* **21**, 651–60 (2007).
6. Verdolini Abbott, K. *et al.* Vocal exercise may attenuate acute vocal fold inflammation. *J. Voice* **26**, 814.e1–13 (2012).

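### Every dependent measure is tested at .05 with no primary measure, decisive contrast or control across measures, so the study-wide false-positive rate exceeds 5%

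*Combined protocol and SAP*

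**What the plan says.** Section A (Proposed Research Rationale) poses a comparison: "we seek to determine if a vocal cool down can mitigate the negative effects of a vocally tiring task as compared to vocal rest". It adds that voice and respiratory measures are repeated in order to identify mechanisms.

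Section B describes what is collected. "Videostroboscopy, voice measures and respiratory measures will be collected at 4 different times on each day". Within the voice family, "Participants will be asked to glide up and down their pitch range", "We will also collect the air pressure used for speaking and singing", and "participants will use visual analog scales to rate how they feel about their voice". The respiratory family comes from bands on the rib cage and abdomen.

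Section J gives one sentence for all of this: "Dependent measures will be analyzed using linear mixed effect models". The model has time (four levels), strategy (two levels), their interaction and a random participant effect. "Alpha level for significance will be set at" p < .05. Post-hoc comparisons use Tukey HSD. N = 30 is said to give reasonable power, with no outcome, effect size, SD, correlation or power level attached.

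**The concern.** The plan fits the same model to an unlisted set of measures and gives each one the full .05. Nothing ranks the measures, and nothing says whether the strategy main effect, the interaction or a pairwise comparison answers the Section A question. Followed as written, it lets whichever measure and test reach p < .05 stand as the answer.

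Two features of this trial make the missing hierarchy matter more. Participants know whether they have just stayed silent or done voice exercises, so the visual analog ratings are unblinded, and a positive result could rest on one of them alone. The strategy main effect also averages over baseline and post-exertion 1, both of which precede the strategy, yet Section J does not exclude it as evidence.

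**Working it through.** **Inputs from the document.** Alpha is .05 per test and N = 30, with each participant doing both strategies (Sections B and J). There are at least three measure families (Section B). The number of measures k is not stated. **Assumptions:** k = 3, 5 or 10; one strategy test per measure unless noted; correlation rho between test statistics of 0, 0.5 or 0.8; each test at its nominal level.

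**The plan's own figure.** N = 30 cannot be reproduced, because effect size, SD, correlation, power level and outcome are all absent. As a back-calculation only, with 80% power assumed, the smallest detectable paired standardised difference is (1.960 + 0.842)/√30 = 0.51.

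**Chance of at least one false positive.** For independent tests this is 1 − 0.95^k:

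- k = 3: 1 − 0.857 = 14.3%
- k = 5: 1 − 0.774 = 22.6%
- k = 10: 1 − 0.599 = 40.1%

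For correlated tests, equicorrelated normal statistics were integrated: 1 − ∫ φ(x) [Φ((1.96 − √ρ x)/√(1−ρ)) − Φ((−1.96 − √ρ x)/√(1−ρ))]^k dx. For errors favouring cool down only, each measure contributes 2.5%, so the independent case is 1 − 0.975^k.

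| k | Either direction, rho 0 | rho 0.5 | rho 0.8 | Favouring cool down, rho 0 | rho 0.5 |
|---|---|---|---|---|---|
| 3 | 14.3% | 12.5% | 9.8% | 7.3% | 6.3% |
| 5 | 22.6% | 18.3% | 12.7% | 11.9% | 9.1% |
| 10 | 40.1% | 28.7% | 17.3% | 22.4% | 14.4% |

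**If both the main effect and the interaction count.** The rate per measure is 1 − 0.95² = 9.75%, which gives 26.5%, 40.1% and 64.2% for k = 3, 5 and 10 (independent).

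**Effect of the decision rule.** The Section J model was simulated with no strategy effect (40,000 runs, 30 participants, 2 × 4 cells, random intercept, Tukey HSD over the 8 cells). Per measure:

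- interaction significant: 5.0%
- main effect or interaction significant: 9.7%
- significant interaction and a Tukey-significant cool-down advantage after the strategy or after exertion 2: 0.19%, which is 1.9% over 10 independent measures
- that route, or a significant main effect favouring cool down: 2.7%, which is 23.9% over 10 independent measures

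The unstated decision rule therefore moves the result as much as the unstated number of measures does.

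**The case against.** A reader might infer that a false claim for cool down is likely, or that the error rate is far above .05. The documents do not support either. Section J gives no count, and much of Section B describes elicitation tasks rather than analysed outcomes; loudness and pitch levels could be conditions of a single measure. Only the three families are firm, so a count of 8 to 10 would be inference. The either-direction percentages also include errors favouring rest. Errors favouring cool down pass 50% only at 28 independent measures, and later with correlation. The interaction has 3 degrees of freedom and no direction, so rejecting it does not in itself say that cool down works. If Tukey-significant superiority is also required, the rate is small. All of this stands and limits the size of the point.

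It can also be said that the study is small and partly mechanistic, that Section J speaks of study questions in the plural, and that strict control over every measure is a matter of preference. That is fair for the mechanistic measures, which is why they can be labelled exploratory. It does not cover the cool-down versus rest comparison.

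A reader might further infer that an instrumental measure such as air pressure ought to be primary. The documents do not show this. Air pressure is taken at different loudness and pitch levels, so it is not yet one variable, and Section A motivates the study by vocal fatigue and effort, which self-ratings may reflect more directly.

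Finally, Section A says the trial will be registered, and a primary outcome may be named there. That record was not available, and Section J does not refer to one.

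**Conclusion.** The concern holds in limited form. With no primary measure, no decisive contrast and no control across measures, Section J leaves the study-wide false-positive rate above 5% by an amount that depends on choices it does not state. At three independent measures, one per family, the chance of any false positive is 14%, about half of it favouring cool down (7%). At ten it is 40% if independent and 29% at correlation 0.5. These figures rest on assumed counts and correlations, one strategy test per measure and a correctly specified random-intercept model. They fall sharply under a rule requiring both a significant interaction and a Tukey-significant advantage, and they rise if the main effect and the interaction both count. Because Section J adopts neither rule, no single error rate can be given.

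**What to change.** In Section J:

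1. Name one primary measure from those already collected, defined as a single variable (including loudness and pitch level where relevant). The investigators should choose and justify it, noting that self-ratings are unblinded.
2. Name one time point and one strategy contrast for it, tested at .05, and state that the cool-down versus rest conclusion rests on that test. The measurement after the strategy and the one after the second exertion answer different questions, so the choice should be explicit.
3. List the secondary measures and apply Holm across them. They may support the primary result but not replace it.
4. Label the remaining mechanistic measures exploratory.
5. Tie the N = 30 power statement to the primary contrast, with its effect size, SD, within-participant correlation and power.

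The primary test then carries a 5% two-sided error, 2.5% in favour of cool down, with no loss of power from multiplicity. No new data are needed, but the power calculation must be restated. The downside is a stricter threshold for secondary measures. Holm's first step with m measures is .05/m, so at N = 30 and 80% power the detectable paired difference for that step rises from 0.51 to 0.59 (m = 3), 0.62 (m = 5) or 0.67 (m = 10).

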The study design will be a within-participant, repeated measures design. Once subjects are screened (see below), they will be scheduled to participate on two consecutive days. The procedures will be similar on both day. In brief, voice and respiratory measures will be collected on each day. Subjects will then perform a vocal exertion task and voice and respiratory measures will be collected again. The subjects will perform a cool down or vocal rest. Voice and respiratory measures will be collected again, followed by a second vocal exertion task and re-collection of voice and respiratory measures.

Because this study meets the NIH definition of a clinical trial, this study will be registered on ClinicalTrials.gov. A description of this clinical trial will be available on <http://www.ClinicalTrials.gov>, as required by U.S. law, once the IRB is approved.

B. SPECIFIC PROCEDURES TO BE FOLLOWED

The proposed methodologies are routinely used in our laboratories. All proposed methodologies have been previously approved by the Purdue IRB. In addition, all devices utilized in this study are commercially available and will be used in accordance with their approved label.

[figure not shown]
Protocol and Research Design:

Phone Screening and scheduling: verbal consent will be obtained before any questions will be asked over the phone. Once consent is obtained, screening questions will be asked (Document A). If subjects meet exclusion

criteria they will not be scheduled. If subjects are willing and able to participate, they will be asked to come back to the lab on two consecutive days at roughly the same time of day and will be scheduled.

Day 1: Informed consent will be obtained. Next, participants will complete a questionnaire (Document B) asking about current health status, medical history, medications, and occupational voice use. Then, participants will complete the Vocal Fatigue Index (Document C), the Vocal Handicap Index (VHI) (Document D) and the Reflux Symptom Index (RSI, Document E). Overall, these data will provide us a complete understanding of each participant's medical history, voice use, perception of voice and occupational voice needs. Then subjects will be scheduled for the following procedures if they are willing and available. Partial payment will not be provided if they are unwilling or unable to participate in the following procedures.

A schematic of the research design is shown below:

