Vocal Exertion Task: Next, subjects will complete the second vocal exertion task for the same duration or shorter duration as the first task.

Measures: Videostroboscopy, voice measures, and respiratory kinematics will be obtained.

C. SUBJECTS TO BE INCLUDED

Participants will include males and females > 18 years with normal speech and language. Inclusion and exclusion criteria are listed below.

Exclusion criteria: Individuals will not be included in this study if they report cognitive impairments or disorders, craniofacial disorders (i.e., cleft palette or submucosal cleft), head and neck cancer, hearing difficulties, or have dentition problems or dentures which limit laryngeal imaging. Subjects will also be excluded if they report a gag reflex when they brush their teeth or refuse to undergo laryngeal imaging.

Inclusion criteria: Participants must be within the appropriate age range (18-65 years at the time of study) to participate in this study. They must score $\geq 80\%$ for their age, weight, height and race on forced vital capacity and forced expiratory volume in 1.0 second on spirometry. In addition, the investigators must be able to obtain an image of the individual's larynx using rigid endoscopy to ensure that no gross laryngeal pathology is present. The presence of any pathology will preclude participation.

If any pathology is observed suggestive of an underlying condition, the subject will be referred back to their physician and will not be included in the study.

Participant availability and plan for dropout: We do not anticipate any difficulty in recruiting adults. We will recruit participants through fliers posted on campus and surrounding communities, ads in Purdue Today or similar newsletters, word of mouth, email, or phone. If participants drop out of the study before the end, they will be paid a partial payment and we will recruit a new participant to replace them.

D. RECRUITMENT OF SUBJECTS AND OBTAINING INFORMED CONSENT

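### The analysis model for a two-day counterbalanced crossover has no day term: a day effect costs power, and with unequal orders it leaks into the strategy main effect

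*Combined protocol and SAP*

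**What the plan says.** Section B of the combined protocol and SAP describes a two-period crossover. Participants attend "on two consecutive days at roughly the same time of day", and the allocation of strategy to day is stated as "Participants will be counterbalanced to cool down or vocal rest such that each participant will complete both on different days". Neither the method of counterbalancing nor the number per order is given. Measures are taken four times on each day, so each participant has 8 observations.

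Section J gives the model: "Fixed factors included in the statistical model will include time" (four levels) and restoration strategy (two levels). It adds "A time and restoration strategy interaction will also be included in the model", and participant is the random factor. No section mentions day, period, order or sequence as a model term.

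On dropout, Section C says "we will recruit a new participant to replace them" and gives no rule for the replacement's order. On sample size, Section J says "Power analysis indicates an N of 30 subjects will be sufficient to answer study questions with reasonable statistical power". It gives no effect size, SD, correlation or target power.

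**The concern.** Outcomes may differ between the two days for reasons unrelated to strategy. Screening is by phone, so day 1 is the participant's first study visit, with the first study endoscopy, mask, respiratory bands and loud-voice task. Day 2 follows the next day, after two exertion tasks. Practice, familiarity and leftover fatigue could each shift the measures, including the self-ratings. Scheduling at a similar hour controls time of day, but none of these.

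Counterbalancing protects the strategy estimate from a day shift only while the orders are equal. Even then it does not take the shift out of the error term; only a day term in the model does that. Two things are at stake:

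- **Power.** Both tests of strategy lose power. The sample size is justified only in general terms, so no margin is stated to absorb the loss.
- **Bias, if orders become unequal.** Part of the day shift would be read as a strategy effect in the main effect and in strategy comparisons at a single time.

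The aim in Section A is "we seek to determine if a vocal cool down can mitigate the negative effects of a vocally tiring task". The time-by-strategy interaction is the closest test of that. A constant day shift cannot bias it; only a shift that changes across the four times can.

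**Working it through.** The plan's own figure, N = 30, cannot be reproduced because its inputs are not given. The check therefore sets effects that give 80% power when there is no day shift, and asks what a shift does.

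**Inputs from the documents.** 30 participants × 2 days × 4 times = 240 observations; alpha 0.05; the model in Section J.

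**Assumptions.** Complete data, independent residuals with SD 1, no participant-by-day variance. The day shift δ is 0.5 or 1.0 residual SD.

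**Degrees of freedom.** The plan's model uses 30 (participant) + 3 (time) + 1 (strategy) + 3 (interaction) = 37, leaving 240 − 37 = 203. Day and day-by-time use 1 + 3 = 4 more, leaving 199.

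**Equal orders, constant shift.** The shift adds 60δ² to the residual sum of squares, so the residual mean square is 1 + 60δ²/203:

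- δ = 0.5: 1 + 15/203 = 1.07
- δ = 1.0: 1 + 60/203 = 1.30

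The true variance of the strategy estimate is still 2/120 = 1/60. The test divides by too large an error, so it is conservative under the null and loses power under the alternative. As a closed-form check for the main effect, the 80%-power effect is 0.363 SD, or 0.363 × √60 = 2.81 standard errors. The critical value on 203 df is 1.972. With δ = 1.0 it becomes 1.972 × √1.296 = 2.24, so power is about Φ(2.81 − 2.24) = Φ(0.57), or roughly 71 to 72%. Simulation (20,000 runs per cell) agrees:

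| 15/15, constant δ | 0 | 0.25 | 0.5 | 1.0 |
|---|---|---|---|---|
| Main-effect power | 0.798 | 0.796 | 0.778 | 0.712 |
| Interaction power | 0.799 | 0.791 | 0.773 | 0.666 |

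The interaction effect used is a strategy difference of 0.861 SD at the last two times only. With day and day-by-time added, power is 0.797 to 0.800 (main effect) and 0.799 to 0.805 (interaction) for every δ. If the shift appears only after baseline, interaction power without the day terms is 0.776 (δ = 0.5) and 0.701 (δ = 1.0).

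**Unequal orders.** The bias in the strategy main effect is δ(n1 − n2)/30. Simulated main-effect type I error under the plan's model:

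| Orders | Share of day shift | δ = 0.5 | δ = 1.0 |
|---|---|---|---|
| 15/15 | 0 | 0.043 | 0.027 |
| 16/14 | 2/30 = 7% | 0.048 | 0.047 |
| 17/13 | 4/30 = 13% | 0.068 | 0.117 |
| 18/12 | 6/30 = 20% | 0.110 | 0.250 |

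With the day terms, these values are 0.047 to 0.052. Interaction type I error under the plan's model stays at or below 0.05 through 18/12: 0.017 to 0.040 for a constant shift and 0.022 to 0.049 for a post-baseline shift.

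**How likely are unequal orders?** Start from 15/15, with m dropouts equally likely from either order and each replacement given an order at random. The net movement is then Binomial(2m, ½) − m. The chance of 17/13 or worse is 2/16 = 13% for m = 2, 74/256 = 29% for m = 4, and 1588/4096 = 39% for m = 6. The chance of 18/12 or worse is 0, 18/256 = 7% and 598/4096 = 15%.

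**Participant-by-day variance.** If participants also vary from day to day with an assumed SD of 0.5, main-effect type I error at 15/15 with no day shift is about 0.14, with or without a day term. With a 1.0 SD shift, adding the day terms moves it from about 0.09 to 0.14 at 15/15, and from 0.28 to 0.14 at 18/12.

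**The case against.** The strongest reply accepts the omission and disputes its weight.

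- **Size.** With counterbalancing done as written there is no bias, and at a 0.5 SD shift the power loss is only 2 to 3 points. The larger losses need a shift of a full residual SD, and the documents give no day effect of any size. This stands, and it limits how strongly the point can be put.
- **Stacked conditions.** The bias needs a day shift, dropouts and replacements that do not keep the original order; replacing a dropout could fairly mean filling the same slot. This also stands. The bias is a possibility, and one sentence in the plan would close it.
- **Target.** The main effect averages in two time points that precede the strategy, so it is a weak measure of the aim, and the interaction is not biased by a constant shift. That is correct, but the interaction still loses power.
- **Residual structure.** With a participant-by-day random effect in the model and no fixed day term, interaction power under a constant 1.0 SD shift stays near 79%. Part of the interaction loss therefore reflects that missing random effect. At 15/15, adding day alone can raise main-effect type I error from 0.09 to 0.14 when such variance exists. However, the lower figure arises only because an inflated residual happens to mask a separate omission. At 18/12 the day terms halve the error rate, from 0.28 to 0.14.
- **Day-by-time.** Day alone restores interaction power to 80% or 78% for a post-baseline shift of 0.5 or 1.0 SD, so the further gain from day-by-time is small.

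The listed factors could be read as non-exhaustive, but Section J goes on to name the interaction and the random factor and still leaves out day.

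**Conclusion.** The concern holds. The model in Section J omits a factor that the design creates and that is known for every observation. At 15/15 the cost is lost power only: 2 to 3 points at a day shift of 0.5 residual SD, and 9 to 13 points at 1.0. If the orders become unequal, the strategy main effect and single-time comparisons take in a share (n1 − n2)/30 of the day shift. Main-effect type I error is then 0.07 or 0.12 at 17/13, and 0.11 or 0.25 at 18/12. The interaction is not biased by a constant shift at any split.

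These sizes rest on an assumed day shift, an assumed order split, independent residuals and no participant-by-day variance. In particular, the return to a type I error near 0.05 with the day terms holds only under that last assumption. The change should be made because it improves the model at almost no cost; the point does not show that the planned analysis is invalid.

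**What to change.** In Section J, add day (1 or 2) and day-by-time as fixed effects. In Section C, state that a replacement participant takes the order of the person replaced. As a descriptive check, report the day 2 minus day 1 baseline difference by first-day strategy.

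An order term is not needed for the strategy contrast, because order is constant within a participant and adds nothing once participant is accounted for. Two problems remain after this change. A day term does not remove carry-over that depends on the day 1 strategy. It also does not supply a participant-by-day random effect, which should be considered separately.

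The cost is 4 of 203 residual degrees of freedom and one sentence, with no new data. If there is no day effect, simulated power at 15/15 changes by no more than 0.1 percentage point. At unequal splits the variance of the strategy contrast rises by the factor 1/(1 − s²), with s = (n1 − n2)/30: 0.4% at 16/14, 1.8% at 17/13 and 4.2% at 18/12.

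### The strategy main effect in Section J is diluted by two pre-strategy time points; name the post-strategy contrasts as the tests and use the pre-strategy values to adjust them

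*Combined protocol and SAP*

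**What the plan says.** Section J states that "Dependent measures will be analyzed using linear mixed effect models". The fixed factors are "time (baseline, post exertion task 1, post restorative strategy, post exertion task 2) and restoration strategy (controlled phonation or vocal rest". It adds: "A time and restoration strategy interaction will also be included in the model". The only random term named is the participant: "Participant will be included as a random factor in order to control for individual variation". Post-hoc comparisons use Tukey HSD at an alpha of 0.05. No covariate is listed, and Section J does not say whether the main effect, the interaction or a particular cell comparison answers the study question.

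The order of events is in Section A. After the first measures, "Subjects will then perform a vocal exertion task and voice and respiratory measures will be collected again". Only then comes the strategy: "The subjects will perform a cool down or vocal rest. Voice and respiratory measures will be collected again". Section B confirms the count: "Videostroboscopy, voice measures and respiratory measures will be collected at 4 different times on each day". So each day gives two sets of measures before the strategy and two after it.

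**The concern.** A value measured before the cool down or rest cannot carry that day's strategy effect. Crossing strategy with all four times has two consequences.

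- The strategy main effect averages the real differences with two that are zero in expectation. Anyone who reports it as the effect of cool down against rest understates that effect.
- The two pre-strategy values are natural predictors of the same day's later values, but they enter only as further outcomes. Error that they could remove stays in the comparison that answers Section A's question, in a study of 30 people.

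**Working it through.** **The plan's own figure.** Section J says that 30 participants suffice but gives no effect size, SD, correlation, numerical power or primary measure, so the figure cannot be reproduced. Solving backwards, a two-sided 0.05 paired t-test with N = 30 has 80% power for a mean difference of 0.53 SDs of the paired difference.

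**Assumptions used below (not in the documents).** Within-participant SD is 1 per measurement, same-day correlation is ρ after removing the participant, there is no strategy effect at the two pre-strategy times, and the true difference d is 0.6. A paired difference then has variance 2, so 0.6 is 0.6/√2 = 0.42 SDs of the difference.

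**Step 1: dilution of the main effect.** This needs no variance assumption.
- Equal effect at both later times: (0 + 0 + d + d)/4 = d/2, so 0.6 becomes 0.30.
- Effect only right after the strategy: (0 + 0 + d + 0)/4 = d/4, so 0.6 becomes 0.15.

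The cell difference at each post-strategy time, which the interaction model also estimates, has the full expectation d.

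**Step 2: what each term can detect at ρ = 0** (participant random intercept; residual df 240 − 30 − 7 = 203).

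| Term | Effect at both later times | Effect right after strategy only |
|---|---|---|
| Main effect, 1 df | 30 × 0.36/2 = 5.4; power 64% | 60 × 0.15² = 1.35; power 21% |
| Interaction, 3 df | 15 × 4 × 0.3² = 5.4; power 46% | 15 × (3 × 0.15² + 0.45²) = 4.05; power 36% |
| Average of the two later times, 1 df | 30 × 0.36 = 10.8; power 91% | 30 × 0.3² = 2.7; power 37% |

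The first figure in each cell is the noncentrality. When the effect is at both later times, the main effect has half the noncentrality of the post-strategy contrast.

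**Step 3: gain from adjustment, for the contrast right after the strategy.**
- Unadjusted: SE = √(2/30) = 0.258 at every ρ.
- Adjusted for both pre-strategy differences, slopes known: the variance is multiplied by 1 − 2ρ²/(1 + ρ), which is 1.00, 0.86, 0.67 and 0.42 at ρ = 0, 0.3, 0.5 and 0.7. With slopes estimated, the simulated SD is 0.249, 0.218 and 0.172 at ρ = 0.3, 0.5 and 0.7.
- Subtracting the mean of the two pre-strategy times: variance = 2 × [1 + (1 + ρ)/2 − 2ρ]/30 = (1 − ρ)/10, so SE = 0.316, 0.265, 0.224 and 0.173. This beats the unadjusted SE only when (1 − ρ)/10 < 2/30, that is ρ > 1/3.

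| ρ | Adjusted power | Unadjusted power | Minus pre-strategy mean |
|---|---|---|---|
| 0 | about 58% | about 61-62% | SE 0.316, clearly worse |
| 0.3 | about 65% | about 61-62% | about 59% |
| 0.5 | about 75% | about 61-62% | about 73-74% |
| 0.7 | about 92% | about 61-62% | about 92% |

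**Step 4: a trap in the adjustment.** If the pre-strategy differences are centred at their sample means, the intercept becomes the raw mean difference (simulated SD about 0.26 at every ρ), while its reported standard error still shrinks. Type I error is then about 6.6%, 10.8% and 18.4% at ρ = 0.3, 0.5 and 0.7. With uncentred differences it is about 5%.

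**Step 5: the error term.** With participant as the only random term and real day-to-day variation, the main-effect test rejects a true null 18%, 27% and 35% of the time when the day's share of variance is 0.3, 0.5 and 0.7. The interaction test rejects 2.3%, 0.7% and 0.1% of the time. A mixed-model version of the fix therefore has to model same-day correlation.

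**The case against.** Modelling all four times with an interaction is valid and conventional. It describes the course of exertion and recovery and allows a check of balance before the strategy. Nothing in Section J says that the main effect will be taken as the answer.

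A reader might infer that the plan shrinks the strategy effect throughout. The documents do not support that: the interaction is in the model, and its post-strategy cell contrasts estimate the full effect. Nor is it an error in itself to keep pre-strategy values as outcomes. A model that holds the strategy difference at zero before the strategy does so, and is about as efficient as covariates.

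A reader might also infer that naming a contrast would not help, or that adjustment always brings a large gain. Neither holds. Naming a contrast recovers much of the loss: the simulated power of Tukey HSD over all eight cells (8 × 7/2 = 28 pairs) is about 31%, 35% and 41% at ρ = 0.3, 0.5 and 0.7, against 61-62% for the single unadjusted contrast. A fixed subtraction of the pre-strategy mean nearly matches adjustment at ρ of 0.5 to 0.7. Gains measured against change from post exertion task 1 would look larger, but Section J specifies no such change score.

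What remains is that the main effect is diluted by construction, no term is named as the answer, and measurements already collected are not used to reduce error.

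**Conclusion.** The point holds as a matter of which term to read and of precision, not as a bias in the whole analysis. The dilution to d/2 or d/4 follows from the order of measurement and requires only that the strategy has no effect before it is given. The power figures rest on the assumed SD, the assumed difference of 0.6 and an unknown same-day correlation. Compared with an unadjusted post-strategy contrast, adjustment costs about 3 to 4 percentage points of power at ρ = 0, gains about 3 to 4 at 0.3, about 13 to 14 at 0.5 and about 30 at 0.7. These figures are for one contrast tested at 0.05.

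**What to change.** In Section J:

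- Name the cool-down-minus-rest contrasts at post restorative strategy and at post exertion task 2 as the tests of the strategy question, and state how alpha is handled across the two.
- State that the strategy main effect will not be used as evidence of a strategy effect.
- Estimate each contrast by regressing the participant's difference (cool-down day minus rest day) on the baseline and post exertion task 1 differences, uncentred, with order coded +1/−1. The intercept is the strategy effect. Do not centre the differences at their sample means.
- Alternatively, fit a mixed model with a day or order term and same-day correlation that constrains the strategy difference to zero at the two pre-strategy times.
- Keep the four-level time factor to describe the course.

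The cost is a few lines of SAP text and SAS code, with no new data. The covariates use two error degrees of freedom. Day 2 follows the other strategy on day 1, so any carry-over would enter the day 2 pre-strategy values. The SAP should state this limitation.
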